7.2 Protocol Deviations

A summary of protocol deviations will be presented by the deviation category, reason, and treatment group in Table 10.2.1(a)(b)(c)(d). This table will provide both the number of participants and the number of deviations for each category and treatment group.

All participant-specific and non-participant-specific protocol deviations will be included as data listings (Listings 16.2.2.1(a)(b)(c)(d) and 16.2.2.2(a)(b)(c)(d), respectively).

7.3 Demographic and Other Baseline Characteristics

Summaries of sex, ethnicity, and race will be presented by treatment group and overall in Tables 14.1.4.1 (a)(b)(c)(d) for all participants in the Safety population. Participants may self-designate as belonging to more than one race or may refuse to identify a race, the latter reflected in the CRF as "No" to each racial option. Participants belonging to more than one race will be categorized as multi-racial and

participants refusing to identify with a race will be classified as unknown on the table. Age will be summarized in years for adults and in months for toddlers, younger children and infants. Age, height and weight will be summarized by treatment group and overall in Tables 14.1.4.2(a)(b)(c)(d).

Individual participant listings will be presented for all demographic and baseline characteristics (Listings 16.2.4.1(a)(b)(c)(d)).

7.4 Concurrent Illnesses and Medical Conditions

All current illnesses and past pre-existing medical conditions will be MedDRA coded using MedDRA dictionary version 19.1 or higher. Summaries of participant's pre-existing medical conditions will be presented by MedDRA® SOC and treatment group (Tables 14.1.5(a)(b)(c)(d)) for all participants in the Safety population.

Individual data listings will be presented for all pre-existing medical conditions (Listings 16.2.4.2(a)(b)(c)(d)).

7.5 Measurements of Treatment Compliance

All participants were to receive 2 doses of study product administered in the clinic. Any participants who were enrolled but did not receive both vaccinations will be presented by treatment group and by site as part of the participant disposition table (Table 14.1.3(a)(b)(c)(d)). A summary of the dates of vaccination will be presented by treatment group in Table 14.1.6(a)(b)(c)(d)).

8 IMMUNOGENICITY EVALUATION

The secondary and exploratory immunogenicity analyses are based on the ALS assay, ELISA assay and fecal assays. Whole blood and plasma specimens will be collected for immunogenicity assessments at Screening, Day 7 and Day 19. Fecal specimens will be collected for immunogenicity assessments at Screening, Day 1, Day 7, Day 19 and Day 29. All immunogenicity analyses will be conducted using the FA and the PP populations, unless they are the same. The number of participants in a population may vary by antigen and assay type as only participants contributing assessments will be included in the population for a specific antigen and assay. Individual participant data listings of immunogenicity will be presented in Listings 16.2.6.1(a)(b)(c)(d) - 16.2.6.3(a)(b)(c)(d) for ALS, fecal, and plasma, respectively.

Pairwise comparisons between each dose of the vaccine without dmLT, and each vaccine co-administered with dmLT adjuvant dose and placebo will be performed for each age-group: adults, toddlers (24-59 months), younger children (12-23 months), and infants (6-11 months). In addition, pairwise comparisons will be made between the combined vaccine without dmLT group and the combined vaccine with dmLT as well as comparisons of these two group with placebo.

Due to the hypothesis generating nature of multiple statistical comparisons for immunogenicity associated with multiple endpoints for this age and dose escalating study, all estimations will be carried out using a two-sided 5% Type I error rate. For each immunogenicity endpoint and antigen analyzed, a Holm's-Bonferroni correction will be applied to determine significance.

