3.1.2 Secondary Objective

The secondary objectives deal with immunogenicity and are the following:

- To assess vaccine induced IgA antibody responses in lymphocyte secretions by the ALS assay against LTB, CFA/I, CS3, CS5 and CS6 in descending age-groups
- To evaluate vaccine induced fecal secretion IgA (SIgA) antibody responses against CFA/I, CS3, CS5, CS6, O78 LPS and LTB in applicable age-groups in Bangladesh
- To assess vaccine induced plasma IgA antibody responses against LTB, O78 LPS, CFA/I, CS3, CS6 and CS5 and IgG antibody responses against LTB and O78 LPS
- To evaluate vaccine induced ALS IgA responses against O78 LPS (if sample volume allows)
- To assess adjuvant effect of dmLT on vaccine immune response compared to responses when giving vaccine alone in descending age-groups in Bangladesh

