4.3 Selection of Study Population

This will be a single site study conducted at the Mirpur field site by the icddr,b. The first part (Part A) will enroll a total of 45 adult participants (30 vaccinees and 15 placebos) into one Cohort. The second part (Part B) will enroll a total of 150 toddlers (24-29 months) into 6 separate cohorts to be recruited in step-wise

fashion. Each cohort will enroll 25 toddlers (15 vaccinees and 10 placebos). The third part (Part C) will enroll a total of 100 younger children (12-23 months) into 4 separate cohorts in a step-wise fashion. Each cohort will enroll 25 younger children (15 vaccinees and 10 placebos). The fourth part (Part D) will enroll a total of 200 infants (6-11 months) into 5 separate cohorts to be recruited in a step-wise fashion. Each cohort will enroll 40 infants (30 vaccinees and 10 placebos). Toddlers, younger children and infants will only be enrolled if their parents are fully informed about the study and provide consent for their child's participation.

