4.4.2 Method of Assigning Participants to Treatment Groups (Randomization)

The randomization scheme will be generated and maintained by the Statistical Data Coordinating Center (SDCC) at the Emmes Corporation, Rockville, MD. Randomization will occur manually on the day participants are to receive their first study vaccination, after confirmation of eligibility and immediately prior to immunization. The unblinded study pharmacist or member of the IP formulation team will be provided with the treatment assignment codes for preparation of the vaccine or placebo to be given to each participant. The unblinded study pharmacist (or designee) will maintain the treatment code list in a secure place. Each participant's treatment assignment will be entered into the AdvantageEDCSM system at Emmes after product administration has occurred.

Eligible participants were randomized and assigned as shown below. The doses shown in **bold** are the highest safe doses chosen by the IPST. Where appropriate, all tables and figures will report the actual dose received.

- Part A: Adults 1:1:1 ratio Cohort A1
 - Full dose ETVAX only
 - Full dose ETVAX + 10 μg dmLT
 - o Placebo
- Part B: toddlers aged 24 59 months,
 - o Cohort B1 3:2 ratio
 - 1/4 dose ETVAX only
 - Placebo

- o Cohort B2 3:2 ratio
 - 1/2 dose ETVAX only
 - Placebo
- Cohort B3 3:2 ratio
 - Full dose ETVAX only
 - Placebo
- o Cohort B4 3:2 ratio
 - Highest safe dose ETVAX (1/2 dose) + 2.5μg dmLT
 - Placebo
- Cohort B5 3:2 ratio
 - Highest safe dose ETVAX (1/2 dose) + 5μg dmLT
 - Placebo
- Cohort B6 3:2 ratio
 - Highest safe dose ETVAX (1/2 dose) + 10μg dmLT
 - Placebo
- Part C: younger children aged 12 23 months,
 - o Cohort C1 3:2 ratio
 - 1/4 dose ETVAX only
 - Placebo
 - o Cohort C2 3:2 ratio
 - 1/2 dose ETVAX only
 - Placebo
 - Cohort C3 3:2 ratio
 - Highest safe dose ETVAX (1/2 dose) + 2.5µg dmLT
 - Placebo
 - o Cohort C4 3:2 ratio
 - Highest safe dose ETVAX (1/2 dose) + 5µg dmLT
 - Placebo
- Part D: infants aged 6 11 months,
 - Cohort D1 3:1 ratio
 - 1/8 dose ETVAX only
 - Placebo
 - O Cohort D2 3:1 ratio
 - 1/4 dose ETVAX only
 - Placebo
 - o Cohort D3 3:1 ratio
 - 1/2 dose ETVAX only
 - Placebo
 - O Cohort D4 3:1 ratio
 - Highest safe dose ETVAX (1/4 dose) + 2.5μg dmLT
 - Placebo
 - o Cohort D5 3:1 ratio
 - Highest safe dose ETVAX (1/4 dose) + 5µg dmLT
 - Placebo

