5 μg dmLT vs 10 μg dmLT	0.xxxx	0.xxxx								
Combined Treatment Comparisons										
Combined ETVAX without dmLT vs Combined ETVAX with dmLT	0.xxxx	0.xxxx								
Placebo vs Combined ETVAX without dmLT	0.xxxx	0.xxxx								
Placebo vs Combined ETVAX with dmLT	0.xxxx	0.xxxx								

Programming Note: Continue Table 14.2.2.1(b) for each antigen in the following order: CFA/I, CS3, CS6, CS5, and 078 LPT. For each antigen, the Holm's-Bonferroni correction will be performed. If a p-value is statistically significant after the adjustment, a "*" will be placed next to the p-value.

TABLE 14.2.1.3(c): Comparison of Antibody Response by Antibody Lymphocyte Secretion IgA - Young Children (12 - 23 Months) Full Analysis Population

			F	P-value from F	isher's Exact	Test	
Antigen	Comparison	Baseline to	Post Dose 1	Baseline to	Post Dose 2	Baseline to A	ny Timepoint
		≥2-fold	≥4-fold	≥2-fold	≥4-fold	≥2-fold	≥4-fold
	Comparing Different Doses of ETVAX without dmLT						
	ETVAX 1/2 Dose vs ETVAX 1/4 Dose	0.xxxx	0.xxxx				
	Comparing Different Doses of ETVAX with dmLT						
	ETVAX 1/2 Dose + 5 μg dmLT vs ETVAX 1/2 Dose + 2.5 μg dmLT	0.xxxx	0.xxxx				
	Comparing ETVAX without dmLT with ETVAX with DMLT						
	ETVAX 1/2 Dose vs ETVAX 1/2 Dose + 5 μg dmLT	0.xxxx	0.xxxx				
	ETVAX 1/2 Dose vs ETVAX 1/2 Dose + 2.5 μg dmLT	0.xxxx	0.xxxx				
	ETVAX 1/4 Dose vs ETVAX 1/2 Dose + 5 μg dmLT	0.xxxx	0.xxxx				
LTB	ETVAX 1/4 Dose vs ETVAX 1/2 Dose + 2.5 μg dmLT	0.xxxx	0.xxxx				
LID	Comparing Placebo to ETVAX with and without dmLT						
	Placebo vs ETVAX 1/2 Dose	0.xxxx	0.xxxx				
	Placebo vs ETVAX 1/4 Dose	0.xxxx	0.xxxx				
	Placebo vs ETVAX 1/2 Dose + 5 μg dmLT	0.xxxx	0.xxxx				
	Placebo vs ETVAX 1/2 Dose + 2.5 μg dmLT	0.xxxx	0.xxxx				
	Combined Treatment Comparisons						
	Combined ETVAX without dmLT vs Combined ETVAX with dmLT	0.xxxx	0.xxxx				
	Placebo vs Combined ETVAX without dmLT	0.xxxx	0.xxxx				
	Placebo vs Combined ETVAX with dmLT	0.xxxx	0.xxxx				

^{*} Using Holm's-Bonferroni adjustment within each antigen, the p-value is statistically significant.

Programming Note: Continue Table 14.2.2.1(c) for each antigen in the following order: CFA/I, CS3, CS6, CS5, and 078 LPT. For each antigen, the Holm's-Bonferroni correction will be performed. If a p-value is statistically significant after the adjustment, a "*" will be placed next to the p-value.

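### In Parts B, C and D the supplementary pooled comparison of ETVAX without and with dmLT mixes antigen dose with adjuvant; it needs a dose-matched pooled row beside it or in its place

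*SAP*

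**What the plan says.** Section 3.1.2 of the SAP lists as a secondary objective: "To assess adjuvant effect of dmLT on vaccine immune response compared to responses when giving vaccine alone in descending age-groups".

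Section 4.4.2 shows how dmLT was combined with antigen. In Parts B and C every dmLT cohort is described as "Highest safe dose ETVAX (1/2 dose"; in Part D as "Highest safe dose ETVAX (1/4 dose". The cohorts without dmLT cover 1/4, 1/2 and full dose in Part B, 1/4 and 1/2 in Part C, and three levels in Part D starting from "1/8 dose ETVAX only". Adults received the full dose with or without dmLT.

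Section 8 first plans comparisons of each single dose arm with each dmLT arm and with placebo. It then adds that "pairwise comparisons will be made between the combined vaccine without dmLT group and the combined vaccine with dmLT". The row "Combined ETVAX without dmLT vs Combined ETVAX with dmLT" stands under Combined Treatment Comparisons, the last block of the paediatric comparison shells (Tables 14.2.1.3, 14.2.3.1 and 14.2.6.1, parts b to d). The fecal and plasma tables reuse these shells. The tests are Fisher's exact test and the t-test. Section 6.4 plans no covariates for immunogenicity.

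**The concern.** The row is labelled simply as without against with dmLT, but the two sides also differ in antigen content. If response depends on antigen dose, part of any difference, or all of it, is a dose effect. The row also has the largest sample of the vaccine-to-vaccine comparisons, so it is more likely than the matched rows to reach significance.

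The SAP separates the two factors elsewhere. The vomiting model in Section 9.1.1 has dose and adjuvant as distinct covariates, and its table footnote removes the full-dose recipients. Immunogenicity has neither safeguard. At stake is a statement about dmLT in young children, and possibly toddlers, that the arms in the row cannot support.

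**Working it through.** The SAP gives no figure for this contrast, so there is none to reproduce.

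**Inputs**
- Antigen doses by cohort: Section 4.4.2.
- Vaccinees per cohort: 15 in Parts B and C, 30 in Part D (Section 4.3).
- Full-dose children: the footnote to Tables 14.3.1.6.1 and 14.3.1.6.2 gives n=5. I read this as Part B, the only paediatric Part with a full-dose arm.
- SD 0.6 on the log10 scale (Section 5).
- Fold change in response per antigen doubling, f: not in the SAP. I assume 1.2, 1.5 and 2.

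**Share of the no-dmLT pool at the antigen dose used with dmLT**
- Part C: 15/30 = 50%.
- Part B: 15/45 = 33% as planned; 15/35 = 43% with five full-dose children.
- Part D: 30/90 = 33%.

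**Log-dose offset.** Offset = log2(dose with dmLT) − mean log2(dose without dmLT).
- C: −1 − (−2 − 1)/2 = 0.5.
- B as planned: −1 − (−2 − 1 + 0)/3 = 0.
- B at 15/15/5: −1 − (15×(−2) + 15×(−1) + 5×0)/35 = −1 + 1.286 = 0.286.
- D: −2 − (−3 − 2 − 1)/3 = 0.

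**GMFR ratio, with over without, when dmLT does nothing.** Under a log-linear response this is f^offset.

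| Part | f = 1.2 | f = 1.5 | f = 2 |
|---|---|---|---|
| C | 1.10 | 1.22 | 1.41 |
| B, 15/15/5 | 1.05 | 1.12 | 1.22 |
| B as planned | 1.00 | 1.00 | 1.00 |
| D | 1.00 | 1.00 | 1.00 |

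**If the response is not log-linear.** Suppose it rises up to the dose used with dmLT and is flat above. In Part D only the 1/8 arm, one third of the pool, is then lower, and the ratio is f^(1/3): 1.14 at f = 1.5 and 1.26 at f = 2. If it rises only above that dose, the sign reverses: f^(−1/3) = 0.87 and 0.79. Part B as planned behaves the same way. Part B at 15/15/5 with the plateau gives f^(15/35) = 1.19 and 1.35.

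**Rejection rate of a nominal 5% two-sided t-test with no dmLT effect** (20,000 simulated trials, SD 0.6), at f = 1.5 and f = 2:
- C: 9% and 15%.
- B at 15/15/5, log-linear: 6% and 9%.
- D, plateau: 9% and 16%.

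**Precision of a dose-matched pooled row.** Standard error (SE) ratio, matched to all-dose:
- C, 15 v 30 against 30 v 30: √[(1/15 + 1/30)/(1/30 + 1/30)] = √1.5 = 1.22.
- B, 15 v 45 against 35 v 45: √[(1/15 + 1/45)/(1/35 + 1/45)] = √1.75 = 1.32.
- B as planned, against 45 v 45: √[(1/15 + 1/45)/(1/45 + 1/45)] = √2 = 1.41.
- D, 30 v 60 against 90 v 60: √[(1/30 + 1/60)/(1/90 + 1/60)] = √1.8 = 1.34.

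Power for a 2-fold difference (SD 0.6, unadjusted 5%, no dropout):

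| Part | Existing matched single-arm row | Matched pooled row | All-dose pooled row |
|---|---|---|---|
| C | 26% (15 v 15) | 34% | 48% |
| B | 26% (15 v 15) | 38% | 59% (35 v 45) |
| D | 48% (30 v 30) | 60% | 85% |

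**The case against.** The strongest reply is that the objective is already served. Section 8 puts the single-arm comparisons first and introduces the pooled contrast as an addition. Every paediatric shell has dose-matched rows: 1/2 dose alone against 1/2 dose with each dmLT level in Parts B and C, and 1/4 dose likewise in Part D. Sections 6.8 and 8 call these comparisons exploratory and hypothesis generating. All of this stands, and it limits the defect to one row.

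A reader might infer more in three ways, which the document does not support:
- That the pooled row is the main test of the adjuvant. No section gives it priority, ties it to the secondary objective or attaches a decision to it.
- That all paediatric Parts are biased. On planned numbers and a log-linear response, only Part C has an offset. The toddler figures depend on n=5, which comes from a vomiting-table footnote; the SAP does not say whether those five enter the immunogenicity pool.
- That the toddler pool differs between endpoints, because Table 14.2.1.3(b) has no full-dose rows while Tables 14.2.3.1(b) and 14.2.6.1(b) do. The Fisher shell omits individual rows but does not redefine the pool, and Table 14.2.1.1(b) lists full dose alongside Combined ETVAX Alone. Membership is unstated, not shown to differ.

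What the reply does not remove: no planned row compares the pooled dmLT arms with the same antigen dose alone. The exploratory label excuses multiplicity, but not a row whose title names one factor while two vary.

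**Conclusion.** The point holds for the pooled row only, in Parts B to D. The mixing of antigen dose with adjuvant follows directly from the cohort list and needs no assumption. Its size does: the ratios rest on assumed slopes and, for toddlers, on five full-dose recipients being in the pool. Young children are the clear case, at 1.10 to 1.41 under the assumed slopes. For infants, and for toddlers as planned, the bias is zero under log-linearity and can go either way otherwise. Adults have one antigen dose and no pooled row. It would go too far to say that the SAP cannot assess the adjuvant effect, since its dose-matched single-arm rows do so, though with little power at 15 per arm.

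**What to change.** - Add to the Fisher, geometric mean titer (GMT) and GMFR comparison tables a pooled row matched on antigen dose, and name it as the pooled adjuvant estimate: B2 v B4-B6, C2 v C3-C4, D2 v D4-D5.
- Drop the all-dose row, or label it as not estimating the adjuvant effect.
- State one membership of the combined group without dmLT, including what happens to full-dose toddlers, and apply it to every endpoint.

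The cost is some SAP wording and one contrast per table. The standard error is 22% larger in Part C, 32% in Part B at 15/15/5 (41% at planned size) and 34% in Part D than with the all-dose pool. If the old row is kept with a p-value, the Holm-Bonferroni family grows by one unless that row is declared outside it. The matched row still pools different dmLT doses, and its arms come from sequentially enrolled cohorts, each randomised only against its own placebo. It removes the antigen-dose difference but not any difference between cohorts over time, and a table footnote should say so.

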8.1 ALS Antibodies

For ALS IgA, tables will be presented by antigen in the order of priority as specimen volumes allow. The order of the antigens will be: LTB, CFA/I, CS3, CS6, CS5, and 078 LPS. Immune responses as measured by ALS IgA after each vaccination (Day 7 and Day 19 samples) will be evaluated by the following:

- the percentage of participants achieving an antibody response after the first vaccination (i.e., antibody response is calculated using baseline and Day 7 sample) for LTB, CFA/I, CS3, CS6, CS5 and 078 LPS (if sample available);
- the percentage of participants achieving an antibody response after the second vaccination (i.e., antibody response is calculated using baseline and Day 19 sample) for LTB, CFA/I, CS3, CS6, CS5 and 078 LPS (if sample available);
- the percentage of participants achieving an antibody response after either vaccination (i.e., antibody response observed after either vaccination) for LTB, CFA/I, CS3, CS6, CS5 and 078 LPS (if sample available);
- the geometric mean titer (GMT) of CFA/I, CS3, CS5, CS6, LTB, and 078 LPS (if sample available) at screening and after each vaccination;
- the geometric mean fold rise (GMFR) of CFA/I, CS3, CS5, CS6, LTB and 078 LPS (if sample available) between doses (baseline to post-dose 1 and post-dose 1 to post-dose 2) and from baseline to post-dose 2.

8.1.1 Antibody Response

Percentages of participants with an antibody response at Day 7, Day 19 or at any time point will be calculated along with the corresponding two-sided exact (Clopper-Pearson) binomial 95% CIs. For each antigen, the proportion of participants with an antibody response at Day 7, Day 19 or at any time point will be compared between each pairwise comparison of ETVAX dose level, ETVAX + dmLT dose level, and placebo using Fisher's exact test.

Tables 14.2.1.1 (a)(b)(c)(d) - 14.2.1.2 (a)(b)(c)(d) will summarize the antibody response and 95% CIs for each time period and treatment group by antigen for the FA population and the PP population, respectively. In addition, a Fisher's exact test for each treatment group comparison will be presented for each time period and antigen as shown in Tables 14.2.2.1 (a)(b)(c)(d) - 14.2.2.2(a)(b)(c)(d) for the FA population and the PP population, respectively.

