6.6.1 Safety Oversight

A Data and Safety Monitoring Board (DSMB) will be formed by the Ethical Review Committee (ERC) to evaluate and assess the safety of study participants. In addition, an Independent Protocol Safety Team (IPST) will be formed for the study and will carry out the safety and clinical evaluation of the icddr,b. Moreover there will be a team comprised of the study physician, the Emmes medical monitor, the PI, and the Medical Officer from PATH for evaluation of the study at different intervals during the study.

Before enrolling participants in subsequent cohorts within an age group, the safety data from the previous cohort(s) will be evaluated and reviewed by the IPST. These data include, but are not limited to, physical examinations, vital signs, and solicited reactogenicity symptoms. The IPST will convene after each cohort

within an age group to review data through Day 4 after the second vaccine administration and make a recommendation to the Sponsor on whether to proceed to the initiation of the following cohort.

The DSMB will be composed of 3-4 members, two of which are nominated by the ERC chairperson. The PI also has the option of nominating 1-2 members with therapeutic expertise. The DSMB meets before study initiation, prior to age de-escalation, and after the study closeout. The PI can also request a DSMB meeting depending upon the study complexity or in light of study concerns. The DSMB will advise the PI of its findings and provide recommendations. The DSMB will review all unanticipated problems involving risk to the participants or others, serious adverse events, and all participant deaths associated with the protocol. The PI will inform the Emmes Medical Monitor and the PATH Medical Officer in detail about the discussions of those meetings.

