9.1.1 Solicited Events and Symptoms

Solicited adverse events will be collected pre-vaccination, 60 minutes post-vaccination and then daily for 7 days after vaccination and graded on a scale of 0 (absent), 1 (mild), 2 (moderate) and 3 (severe). Solicited events include: elevated oral temperature, nausea, vomiting, loose stools, diarrhea, abdominal pain/stomach ache, and acute systemic allergic reaction. Adults will have all events collected. Toddlers (24 - 59 months) will have all events except nausea collected and Younger Children (12 - 23 Months) and Infants (6 - 11 months) will only have oral temperature, vomiting, loose stools, diarrhea and acute systemic allergic reaction collected.

The proportion of participants reporting at least one solicited adverse event within 7 days of any vaccination will be summarized for each solicited adverse event and for any solicited adverse event. The 95% CI calculated using Clopper-Pearson methodology from a binomial distribution (SAS Proc Freq with a binomial option) will be presented (Tables 14.3.1.1(a)(b)(c)(d)).

For each solicited adverse event and for any solicited adverse event, the maximum severity over 7 days after each vaccination will be summarized for the Safety population. The number and percentage of participants reporting each event will be summarized for each treatment group by the maximum severity. For each event the denominator is the number of participants with non-missing data for the specific event (Tables 14.3.1.2(a)(b)(c)(d)).

The number and percentage of participants reporting any solicited adverse event and reporting each individual solicited adverse event will be summarized for each day post vaccination for each vaccination by Treatment group (Tables 14.3.1.3(a)(b)(c)(d)) and severity. The percent of participants reporting any solicited event will be displayed graphically in a bar chart in Figures 14.3.1.4(a)(b)(c)(d)).

Fisher's exact test will be used to compare the proportion of participants with solicited reactogenicity events between each of the vaccine arms with the placebo arms. In addition, the vaccine arms without dmLT will be combined, the vaccine arms with dmLT will be combined and all vaccine arms will be combined and each will be compared to placebo. The results will be summarized in Tables 14.3.1.5(a)(b)(c)(d).

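### In Parts B to D the SAP tests across sequentially enrolled cohorts with no cohort term, so dose and dmLT contrasts are not randomised comparisons and are mixed with calendar period

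*SAP*

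**What the plan says.** SAP 4.3 and 4.4.2 set out the design. Toddlers enter six cohorts: "Each cohort will enroll 25 toddlers (15 vaccinees and 10 placebos". Younger children enter "into 4 separate cohorts in a step-wise fashion", also 15 and 10 per cohort. Infants enter "into 5 separate cohorts to be recruited in a step-wise fashion", with 30 vaccinees and 10 placebos each. Each of these cohorts has a single vaccine arm. Adults differ: "45 adult participants (30 vaccinees and 15 placebos) into one Cohort", randomised 1:1:1.

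Section 6.6.1 separates the cohorts in time: "Before enrolling participants in subsequent cohorts within an age group, the safety data from the previous cohort(s) will be evaluated". In 4.4.2 every cohort without dmLT is listed before the dmLT cohorts of its Part, and the dmLT cohorts use the highest safe dose chosen from the earlier ones.

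The analysis does not carry this structure:

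- Section 8.1.1: responder proportions "will be compared between each pairwise comparison of ETVAX dose level, ETVAX + dmLT dose level, and placebo using Fisher's exact test". Sections 8.2.1 and 8.3.1 repeat this. The titre and fold-rise sections use two-sample t-tests.
- Section 8 also combines the arms without dmLT and tests them against the combined dmLT arms.
- Section 6.4 plans no covariates. The shells (for example Tables 14.2.1.3 and 14.2.3.1) have one placebo group per age group.
- Section 9.1.1 compares solicited events "between each of the vaccine arms with the placebo arms" by Fisher's test. Its vomiting regression includes sex, age group, dose and adjuvant. The word cohort there means the age Part, not the enrolment cohort.

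**The concern.** Randomisation protects only comparisons within a cohort. Two kinds of planned test leave it.

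First, a vaccine arm is tested against placebo recipients who mostly enrolled in other periods. Second, every dose-against-dose and dmLT-against-no-dmLT contrast in Parts B to D compares arms from different cohorts, yet earns the same p-value and significance mark as a randomised comparison. The dose and adjuvant terms of the vomiting model have the same weakness.

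The order of the cohorts makes this systematic for the adjuvant question, which is a stated secondary objective. Any seasonal or secular trend goes straight into the combined dmLT contrast. SAP section 2 itself describes heavy background ETEC exposure in young children, and such exposure can move antibody levels and gut symptoms in placebo recipients too. The concurrent placebos that could reveal this are collected but not used as such.

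**Working it through.** **Inputs.** Arm sizes are as planned in 4.3. The within-group SD of 0.6 log10 is from section 5. The between-cohort SD, tau, appears nowhere in the SAP, so 0.10 to 0.20 log10 is an assumption (1.26- to 1.58-fold).

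**The plan's own figure.** Section 5 states about 73% power for a 2-fold difference between two infant groups of 30, which is itself a cross-cohort contrast. With 27 per group after 10% drop-out the t-test has 44% power (48% with 30). That mismatch is a separate matter and does not affect this point.

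**Share of the trial.** 150 + 100 + 200 = 450 of 495 planned participants are in Parts B to D.

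**Time separation.** Review runs to Day 4 after dose 2, and dose 2 is at about Day 14, so cohorts start at least about 18 days apart. Five toddler gaps make at least about 90 days.

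**Type I error of the planned t-tests with no treatment effect.** The test assumes variance V0, but the true variance has an extra term:

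- Two arms of n: V0 = 2 × 0.36/n, extra 2 × tau².
- Arm against placebo pooled over k cohorts: V0 = 0.36/n + 0.36/(10k), extra tau² × (1 − 1/k).
- Size ≈ 2 × [1 − Φ(1.96 × √(V0/(V0 + extra)))].

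Example, 15 v 15 and tau 0.10: V0 = 0.048, extra = 0.02, √(0.048/0.068) = 0.840, size ≈ 10.0%. Simulating the t-tests gives slightly lower values, shown below. Fisher's test was simulated under the same model, counting a responder as a fold rise of at least 2.

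| Comparison | t-test, tau 0.10 / 0.20 | Fisher, tau 0.10 / 0.20 |
|---|---|---|
| Arms, 15 v 15 | 9.5% / 22% | 3% / 8% |
| Arms, 30 v 30 | 14% / 34% | 6.5% / 18.4% |
| Toddler arm v pooled placebo (15 v 60) | 7.8% / 16% | 4.4% / 8.4% |
| Younger-child arm v pooled placebo (15 v 40) | 7.3% / 14% | 4.5% / 7.8% |
| Infant arm v pooled placebo (30 v 50) | 9.5% / 21% | 6.0% / 12.7% |

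With tau = 0 the t-tests hold 5%, while Fisher runs at about 2 to 4%. T-tests against own-cohort placebo, and contrasts of two arms each corrected by its own placebo, held 5% at every tau.

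**Price of respecting the cohorts (standard-error ratios).**

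- Toddlers, own v pooled placebo: √(1/15 + 1/10) / √(1/15 + 1/60) = 1.41.
- Younger children: √(1/15 + 1/10) / √(1/15 + 1/40) = 1.35.
- Infants: √(1/30 + 1/10) / √(1/30 + 1/50) = 1.58.
- Placebo-corrected contrast of two arms: √(2/15 + 2/10) / √(2/15) = 1.58 in toddlers and younger children; √(2/30 + 2/10) / √(2/30) = 2.0 in infants.

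Power for a 2-fold difference, without drop-out: 22% (15 v 10) or 27% (30 v 10) against own-cohort placebo, and 14% or 16% for placebo-corrected arm contrasts. The unadjusted 30 v 30 test has 48%.

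**The case against.** The strongest reply is that nothing confirmatory depends on these tests. Section 6.8 calls the immunogenicity comparisons exploratory, section 8 calls them hypothesis generating, and 9.1.1 treats the solicited-event tests as a screen. That limits the consequence, but those caveats concern the number of tests. They do not tell a reader that the arms were enrolled at different times.

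Other objections stand in part:

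- **Pooling is not stated in words.** It is inferred from the single placebo group in the shells.
- **The significance mark needs Holm-Bonferroni.** The infant titre shell lists 18 contrasts per antigen. If those 18 are the family, the first step is 0.05/18 = 0.28%, and the 30 v 30 t-test then has a true size of about 2.7 to 15%. This is still inflated, but it is not the nominal-5% figure.
- **Assay batch shifts may cancel.** A multiplicative shift drops out of fold-rise endpoints if a participant's samples are run together, which the SAP does not state. It does not drop out of titres, and period effects drop out of neither.
- **Dates are shown.** Tables 14.1.6 display first-vaccination dates by arm, so the non-overlap will be visible, though not adjusted for.
- **The toddler sizes are planned ones.** A footnote to Table 14.3.1.6.1 records only five full-dose recipients.

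A reader might go further and infer that a period bias exists, that it reaches the adults, or that the t-test inflation applies equally to the quoted Fisher test. The documents support none of these: no cohort difference is reported, adults are randomised concurrently, and Fisher's conservatism absorbs much of a shift.

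**Conclusion.** The point holds for Parts B to D. Cross-cohort dose and dmLT contrasts are non-randomised, the combined dmLT contrast is confounded with calendar period, and no planned analysis uses the concurrent placebo to check for it. The size is unknown because it depends wholly on tau. Under the assumed 0.10 to 0.20 log10, per-comparison type I error at nominal 5% is about 10 to 22% (15 v 15) and 14 to 34% (30 v 30) for t-tests between arms. Against pooled placebo it is about 7 to 16% in toddlers and younger children and 10 to 21% in infants. Responder tests are much less affected, and for 15 v 15 at the lower tau they stay below 5%.

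It may be tempting to conclude that no effect seen only in the unstratified comparison should be claimed. The figures do not justify that bar: with 14 to 27% power in the stratified analyses it would reject most true 2-fold effects. A caveat on interpretation is the proportionate response.

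**What to change.** Keep the pooled analyses and add the following for Parts B to D only:

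- **Arm against placebo.** For titres and fold rises, a linear model with enrolment cohort as a factor, so that each arm is judged against its own placebo. For responders and solicited events, Fisher's test within the cohort for a single arm, and a cohort-stratified exact or CMH test for combined arms.
- **Display.** Placebo results by cohort.
- **Cross-cohort contrasts.** Label dose and dmLT comparisons, and the dose and adjuvant terms of the vomiting model, as non-randomised. For the arm contrasts, print the placebo-corrected difference and its confidence interval alongside as a sensitivity estimate. A cohort term alone cannot separate these arms, because each cohort has only one vaccine arm.
- **Interpretation.** State that an effect seen only in the unstratified comparison is read with that caveat.

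The work is SAP wording and extra output from data already collected. The downside should be written down too: standard errors about 1.35 to 1.6 times as large against own-cohort placebo and 1.6 to 2.0 times as large for placebo-corrected arm contrasts, so the companion checks for period effects and does not replace the pooled result.
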